1.1.3 Previous clinical trials investigating diabetic medications in PD

On the basis of the links between PD and type 2 diabetes mellitus, some of the existing licensed treatments for type 2 diabetes mellitus were thought to potentially have beneficial effects on related pathways of mitochondrial function in PD.

Pioglitazone is a licensed treatment for patients with type 2 diabetes mellitus. It acts to reduce insulin resistance and belongs to the class of thiazolidinediones. It was studied in the NET-PD trial, but failed to show an effect on disease modification in early PD (Investigators, 2015).

Exenatide is a glucagon-like peptide-1 (GLP-1) receptor agonist, already used for the treatment of T2DM. In a single-center, randomized, double-blind, placebo-controlled trial, patients with moderate PD received subcutaneous injections of exenatide 2 mg or placebo once weekly for 48 weeks in addition to their regular medication, followed by a 12-week washout period. This showed positive effects on off-medication motor scores in Parkinson's disease, but it is still unclear if exenatide affects the underlying disease pathophysiology. The conclusion was made that the findings warrant further investigation of exenatide as a potential disease-modifying therapy in patients with PD (Athauda et al., 2017).

Besides exenatide and pioglitazone, other drugs that increase insulin sensitivity, including metformin, pioglitazone and MSDC-0160, have been or are currently being investigated as potential disease-

modifying therapies in patients with PD. MSDC-0160 was shown to inhibit the activities of the mitochondrial pyruvate carrier (MPC) complex and act as an insulin sensitizer without activating peroxisome proliferator-activated receptor- γ (PPAR γ) (Ghosh et al., 2016). The MPC complex is the target of thiazolidinediones. These insulin sensitizers have been suggested to reduce the risk of developing PD and have been shown to be neuroprotective in both in vitro and in vivo models. The use of these agents in patients with T2DM has declined, however, owing to an increased risk of a variety of adverse effects, including fluid retention, weight gain, bladder cancer and other cancers. MSDC-0160, which promises to have fewer adverse effects than the thiazolidinediones, was found to be neuroprotective in various mouse models of PD (Jankovic, 2017).

1.1.4 Intranasal Insulin

Central insulin and central insulin receptors have been established as differing from that of the systemically occurring counter parts that specifically regulate glucose utilization (Zhao and Alkon, 2001). In rodents, insulin receptors and insulin-sensitive glucose transporters are selectively co-localized in brain areas responsible for memory, thus providing a platform for insulin signaling whereby selective increases in cerebral glucose utilization could modulate memory (Craft and Watson, 2004; Watson and Craft, 2003).

Intranasal (IN) delivery offers a non-invasive route to deliver large molecules such as insulin directly to the brain while minimizing systemic exposure. Peptides, proteins, vaccines, drug treatments and ions of various sizes are able to pass along the olfactory and trigeminal nerves and are deposited directly into the CNS without having to pass through the blood brain barrier (BBB), which may degrade or limit the amount arriving at the target (Born et al., 2002; Derad et al., 1998; Dhanda et al., 2005; Garmise et al., 2007; Kern et al., 1997; Perras et al., 1999; Thorne et al., 1995; Thorne et al., 2004). CSF insulin levels in healthy adults have been detected as early as 10 minutes following IN delivery while not measurably increasing systemic blood-glucose levels (Born et al., 2002; Kern et al., 1999). Similar observations of the safety of IN insulin have been made in memory impaired adults (Reger et al., 2006; Reger et al., 2008b).

Clinical investigations of intranasal insulin in Alzheimer's dementia (AD) have demonstrated therapeutic effects impacting memory, attention and cognition without significantly altering serum insulin or glucose levels (Reger et al., 2008). Based on a study by Born et al (2002), a single dose of 40 IU insulin is expected to induce temporary increases in cerebrospinal fluid concentrations of insulin distinctly above the normal level in healthy individuals. Craft and colleagues have demonstrated improved delayed memory and preserved caregiver-rated functional ability as represented by the Alzheimer Disease's Assessment Scale-cognitive subscale (ADAS-cog) and the Alzheimer's Disease Cooperative Study-activities of daily living (ADCS-ADL) scale, respectively in AD and Mild Cognitive Impairment (MCI). In this study, patients were treated with regular insulin 10 and 20 IU twice daily during a four month treatment trial (Craft et al., 2012). In a study by Benedict et al. (2007) with 36 healthy men, word list recall was improved after 8 weeks of treatment with intranasal insulin, using doses of 160 IU per day.

Previous animal studies have demonstrated that intranasal insulin treatment can normalize the production and functionality of dopamine and improves motor impairment in 6-OHDA-induced rat PD models (Pang 2016). Although there are no clinical intranasal insulin studies in PD, there have been previous attempts of using other forms of intranasal treatments in PD. This includes a recent study using intranasal Glutathione in PD (Mischley et al., 2017) and intranasal apomorphine (Dewey et al., 1998; van Laar et al., 1992). All intranasal treatments were well tolerated in this population.

In this study, we aim to investigate which intranasal insulin dose out of three doses and placebo, administered at three different doses or placebo over a 21-day period, is the optimum dosage based on safety and tolerability in Parkinson's disease. A similar design was used in a trial investigating intranasal oxytocin in frontotemporal dementia (Finger et al., 2014). Dosing for the first two groups of this study is based on previously conducted intranasal insulin studies in AD and MCI (Craft et al., 2012; Craft et al., 2017), using daily doses on 20 and 40 IU of intranasal insulin. Higher dose have been found to be safe in healthy adults (Benedict et al., 2007a). Prior studies performed have demonstrated favorable effects of this regimen in the MCI/AD population without peripheral hypoglycemia (Craft et al., 2012).

Furthermore, this clinical trial will investigate exploratory outcomes related to the effect of IN insulin on cognition, mood, apathy and motor performance measured by the MDS- UPDRS (United Parkinson's Disease Rating Scale, (Goetz et al., 2008)). To our knowledge, there are no published clinical trials investigating the use of IN insulin in PD.

1.1.5 Safety of Intranasal Insulin

Novolin R has been approved for subcutaneous or intravenous use since 1991. The most common side effect noted with these two routes is hypoglycemia (Regular Insulin, Drug Monograph). A recent review of safety of Intranasal human insulin trials revealed no safety concerns, with no serious adverse events or symptomatic hypoglycemia in a total of 1092 individuals studied (Schmid et al., 2018). Tables 1 (acute) and 2 (chronic) of this review provide a summary of the human studies with intranasal Insulin. The majority of the studies used regular Insulin (Novolin R or Actrapid, Humulin R, Insuman Rapid, H-insulin 100) with similar excipients and none are believed to be in a range that causes harm (Hamidovic, 2015).

Study of pharmacokinetics of intranasal insulin in mice showed only 3% of intranasal insulin entered the circulation and no peripheral metabolic effects were detected up to a day after intranasal administration (Salameh et al., 2015). Treatment with 40 IU insulin in humans found no significant changes in circulating insulin levels, suggesting that intranasal insulin does not pass into the circulation (Born et al., 2002; Kern et al., 1999). Though some studies with higher doses (160IU [2X the proposed dose in this protocol]) have shown small detectable increase in insulin levels, no significant change in blood glucose levels were noted (Kullmann et al., 2018). Notably, intranasally administered insulin improves memory in healthy adults and Alzheimer's patients without altering blood levels of insulin or glucose (Benedict et al., 2004; Benedict et al., 2007b; Craft et al., 2012; Craft et al., 2017; Reger et al., 2008a; Reger et al., 2008b; Schiöth et al., 2011; Schiöth et al., 2012)

The most common side effect with intranasal insulin administration noted is transient local or nasal irritation. Please refer to Table 3 of the Schmid et al., 2018 review for a summary of the local or nasal effects of Intranasal Insulin in humans. In 2012, Craft et al reported, that number of adverse events was higher for the 20 IU and 40 IU when compared to the placebo group; however, there were no SAE's and mostly minor AEs such as rhinitis were reported (Table 4, (Craft et al., 2012)). Similar minor AEs were reported in the 2017 by Craft et al using intranasal insulin (Supplementary table 2, (Craft et al., 2017)). All the documents are attached. Overall, intranasal insulin at the proposed dose in this protocol, is expected to be safe with limited side effect profile. We plan to monitor the subjects for hypoglycemia and Insulin levels.

2 Summary of Device Description

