
Primary Objectives:
 
 • To determine the safety and tolerability of three different doses of intranasal insulin in patients with Parkinson's disease (PD) 	

Secondary Objectives:
 
 • To evaluate efficacy of intranasal insulin on cognitive functioning in PD • To evaluate efficacy of intranasal insulin on motor function in PD • To evaluate efficacy of intranasal insulin on mood and apathy in PD • To identify which outcome measures are most sensitive to effects of intranasal insulin in PD 	
STUDY DESIGN	
Study Type	Dose-finding
Control Type	None
Study Indication Type	Dose-finding, safety
Blinding Schema	Double blinded
Device	SipNose nasal device
Study Design	randomized, parallel-group, double blind, placebo-controlled
Planned Duration of Subject Participation	8 weeks (Treatment duration: 3 weeks)
PRIMARY ENDPOINTS	

 • Composite safety event of either: a reduction of fasting glucose to <70 mg/dL or an unintended reduction of weight >5% • Pre-post change in safety measures (fasting glucose and weight) • Number of AEs and SAEs 	
SECONDARY ENDPOINTS	

 • Pre-post change in cognitive function measures 	

 • Pre-post change in motor function measures • Pre-post change in mood and apathy measures 	
INVESTIGATIONAL PRODUCTS, DOSE AND MODE OF ADMINISTRATION	
Investigational Product	
Regular insulin (Novolin-R) in 3 different doses and placebo
 
Dose 1, group with 7 participants: 20 IU/IN (10 units IN in one nostril twice daily x 21 days, volume 100 µl)
 
Dose 2, group with 7 participants : 40 IU/IN (10 units IN in each nostril twice daily x 21 days, volume 100 µl)
 
Dose 3, group with 9 participants: 80 IU/IN (20 units IN in each nostril twice daily x 21 days, volume 200 µl)
 
Dose 4, group with 7 participants: placebo (each nostril, twice daily)

SUBJECT SELECTION	
Targeted Accrual	30 subjects. We estimate a need to consent 50 participants in order to reach this goal.
INCLUSION CRITERIA	

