3.1 Primary Objective

- To determine the safety and tolerability of three different doses of intranasal insulin in patients with Parkinson's disease (PD)

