4.1 Primary Endpoints

- Composite safety event of either: a reduction of fasting glucose to <70 mg/dL or an unintended reduction of weight >5%
- Pre-post change in safety measures (fasting glucose and weight)
- Number of AEs and SAEs

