5.1 Drug Administration Training

All subjects and study partners will receive extensive training at each visit regarding home administration of IN insulin using the SipNose during visits 1 and 2 (screening and baseline, respectively). Subjects will be required to administer the dose twice daily; once in the morning and again in the evening (at least 8 hours between doses). Subjects will have the opportunity to immediately do a retrial administration if they are unsuccessful in releasing the study drug intranasally. If the SipNose device is discharged prior to insertion into the nose, then a retrial admission would be indicated. However, if the device is discharged following nasal insertion, then a retrial would not be permitted. The steps to ensure that subjects maintain compliance with the study protocol over 3 weeks include administering the following during the study:

- In-clinic training session during screening and baseline visits
- Phone calls to assess compliance from study coordinator at weeks 1 and 2 (approximately 1 and 2 weeks after baseline visit)

In addition to drug administration training, subjects will be given a daily Drug Diary to record the time and date of each self-administered dose, drug vial number and any comments for study staff. Instructions and training for the Drug Diary will be given to all subjects and study partners at the same times as the drug administration training.

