7.1.3 Phone Visit 1: Safety Check (week 1)

- Study staff phone call to address AEs/SAEs 1 week (\pm 5 days) after visit 2

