7.3.1 Physical Examination

Complete physical examination will be performed at visits 1 and 3, or if the subject withdraws or is withdrawn from the study early. Any abnormalities noted at Visit 1, will be documented as part of the subject's medical history.

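### Nasal irritation is the effect the plan expects most often, but no readable section measures it in a structured way; nasal tolerability is left to general AE enquiry in arms of 7 to 9

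*Combined protocol and SAP*

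**What the plan says.** Section 1.1.5 identifies the expected effect: "The most common side effect with intranasal insulin administration noted is transient local or nasal irritation". It adds that in an earlier trial AEs were more numerous on 20 and 40 IU than on placebo, and were mostly minor, such as rhinitis. The same section then commits to specific monitoring of something else: "We plan to monitor the subjects for hypoglycemia and Insulin levels".

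The primary objective (3.1) is the safety and tolerability of three doses. Of the primary endpoints in 4.1, the one that would register a nasal effect is "Number of AEs and SAEs"; the others concern fasting glucose and weight.

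AE collection is described in general terms:

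- **Calls.** The entry for Phone Visit 1 (7.1.3) reads "Study staff phone call to address AEs/SAEs"; those at weeks 2 and 4 are similar. Section 5.1 and Table 3 add a compliance check at weeks 1 and 2.
- **Clinic visits.** AEs and SAEs are recorded at Visits 2 and 3 (7.1.2, 7.1.5).
- **Diary.** Section 5.1: "subjects will be given a daily Drug Diary to record the time and date of each self-administered dose, drug vial number and any comments".
- **Examination.** Section 7.3.1: "Complete physical examination will be performed at visits 1 and 3", or at early withdrawal. No nasal component is named. Abnormalities at Visit 1 go into the medical history.
- **Table 3.** There is an AE row but no nasal row.

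The eligibility criteria in 6.1.2 address chronic sinusitis, nasal surgery, severe septal deviation and other anomalies. Section 12.2 summarises AEs by group and adds a chi-square test only if a spike is noticed.

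**The concern.** The effects that the plan measures by fixed procedure are those it expects to see little of. Section 7.3.3 calls peripheral hypoglycemia relatively unlikely, yet glucose has timed finger sticks and fasting samples. The effect it expects most often has no specified measurement.

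Three features make this matter. First, the symptom is transient, so examinations at Visits 1 and 3 will tend to miss it. Second, an AE under 11.1 must develop or worsen during the study, which calls for a known state just before dosing. Third, local exposure differs by arm (one nostril in Group 1, both in the others, with listed volumes of 100 or 200 µl), so nasal tolerability could plausibly differ too.

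If staff ask differently from call to call, a dose that often irritates the nose could show few recorded events and be described as well tolerated. Because 12.2 tests only after a spike is seen, under-recording would also keep that step from being triggered.

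**Working it through.** **1. Plan's own figure.** Arms are 7, 7, 9 and 7 (Table 2): 7 + 7 + 9 + 7 = 30, as stated. Section 12.4 declares no power target, so there is no power figure to reproduce.

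**2. Search of the readable text.** Sections 7.1.1 to 7.1.6, 7.3.1 to 7.3.6, Table 3 and 12.2 contain no nasal question, scale, checklist, inspection or nasal baseline. The physical examination nearest to the first dose is at Visit 1. Visit 2 follows within 2 weeks (±5 days), so the gap can reach 14 + 5 = 19 days. No physical examination is listed for Visit 2.

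**3. Chance that an arm records no nasal event.** Let p be the true proportion of participants with a nasal symptom and c the proportion of those who are captured. Both are assumptions; the documents give neither. Then P(none recorded) = (1 − p·c)^n.

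| p | c | 1 − p·c | n = 7 | n = 9 |
|---|---|---|---|---|
| 40% | 100% | 0.60 | 3% | 1% |
| 40% | 70% | 0.72 | 10% | 5% |
| 40% | 50% | 0.80 | 21% | 13% |
| 40% | 30% | 0.88 | 41% | 32% |
| 30% | 100% | 0.70 | 8% | 4% |
| 30% | 50% | 0.85 | 32% | 23% |

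**4. Chance of at least two reports.** With q = p·c, P(at least 2) = 1 − (1 − q)^n − n·q·(1 − q)^(n−1). Take p = 20% and n = 7.

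- Full capture, q = 0.2: 1 − 0.210 − 0.367 = 0.42.
- Half captured, q = 0.1: 1 − 0.478 − 0.372 = 0.15.
- For n = 9 the corresponding values are 0.56 and 0.23.

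**5. What a recorded zero would mean.** The exact two-sided 95% upper limit is 1 − 0.025^(1/n): 41% for 0/7 and 34% for 0/9. One report moves the observed proportion by 1/7 = 14 or 1/9 = 11 percentage points.

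**6. Would full capture separate the arms?** Placebo (7) against the highest dose (9), by full enumeration of the 2×2 tables at two-sided 0.05, with assumed true rates of 10% and 50%:

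| Capture | Chi-square, uncorrected | Fisher exact |
|---|---|---|
| 100% | 0.46 | 0.28 |
| 50% | 0.12 | 0.04 |

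Against 0/7 on placebo, significance needs 4/9 by uncorrected chi-square (p = 0.042) or 5/9 by Fisher (p = 0.034). Better capture helps, but power stays low even for a large assumed difference.

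**The case against.** The strongest reply is that AE collection is more active than it may look. Staff initiate the calls at weeks 1, 2 and 4 and record AEs at Visits 2 and 3. Table 3 repeats the AE row at early withdrawal, and 10.2 adds a follow-up call for those who leave early. A reader might infer that nasal symptoms are captured only when volunteered. The documents do not support that: they do not say how AEs are elicited, in either direction.

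A reader might also infer that there is no nasal baseline at all. That goes too far. The Visit 1 examination, the nasal exclusion criteria (reviewed again at Visit 2) and AE recording from consent (11.2.2) give some information on prior state. It is incidental, and none of it is a required nasal record at Visit 2.

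Recall is a lesser worry than the MoCA floor of 16 suggests. A study partner is trained alongside the participant, the diary is daily with a comments field, and the first dose is given in clinic with finger sticks at about 15 and 30 minutes. Irritation that recurs over 21 days has several chances to be mentioned, which makes very low capture less plausible.

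Finally, some material cannot be seen. The device safety and administration sections are redacted, and CRFs are developed separately (13.7). A nasal prompt there cannot be ruled out. Table 3 is readable, however, and lists none.

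These replies limit the point. They leave standing that the expected effect has no specified measurement and that the method of AE enquiry is unstated.

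**Conclusion.** The point holds as a weakness of measurement. No readable section provides a structured nasal symptom question, a named nasal examination or a nasal record just before the first dose, although irritation is named as the most common effect and tolerability is primary. At an assumed 40% incidence, half capture raises the chance of an empty arm of 7 from 3% to 21%. These figures illustrate sensitivity to capture and do not estimate what will happen in this trial.

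Two broader conclusions should not be drawn. The whole primary comparison does not rest on nasal reporting: 12.2 also covers early withdrawals with reasons, fasting glucose and weight, so only the nasal part of tolerability is affected. Nor would better capture let this trial rank the doses. The plan is openly exploratory and descriptive (12.1, 12.4), and step 6 shows how little power arms of 7 and 9 have. Because description is the trial's main product, describing the expected effect reliably is worth a small change.

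**What to change.** Add one row to Table 3 and one line to each of 7.1.2 to 7.1.6 for a short fixed list of nasal symptoms, for example irritation, discharge, blockage, bleeding and sneezing, each present or absent with a grade. Ask the same list in all four arms:

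- at Visit 2 before the first dose, and again with the post-dose finger sticks;
- at Phone Visits 1, 2 and 3;
- at Visit 3 and at early withdrawal.

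In 12.2, report by arm the number and proportion of participants with a new or worse nasal symptom relative to the pre-dose answer, with exact intervals. Tabulate these solicited events separately from other AEs.

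The cost is a one-page form and one or two minutes at contacts that already take place, with no extra visit or staff. The drawback is that solicited counts will rise in all arms, placebo included, which is why they must be kept apart from other AEs. If a nasal item already sits in the redacted sections or the CRFs, the remaining work is to cite it in Table 3, confirm that it is also asked before the first dose, and add the summary to 12.2.

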2.1 Intranasal SipNose Device Overview

REDACTED

Table 1: REDACTED

2.1.1 Intranasal SipNose Device

REDACTED

2.1.2 SipNose Utility, Reliability, and Safety

REDACTED

2.1.2.1 Utility

REDACTED

2.1.2.2 Reliability

REDACTED

2.1.2.3 Safety

REDACTED

2.1.2.4 Device-Drug Contact and Safety

REDACTED

3 Objectives

3.1 Primary Objective

- To determine the safety and tolerability of three different doses of intranasal insulin in patients with Parkinson's disease (PD)

3.2 Secondary Objectives

- To evaluate efficacy of intranasal insulin on cognitive functioning in PD
- To evaluate efficacy of intranasal insulin on motor function in PD
- To evaluate efficacy of intranasal insulin on mood and apathy in PD

To identify which outcome measures are most sensitive to effects of intranasal insulin in PD

4 Endpoint(s)

4.1 Primary Endpoints

- Composite safety event of either: a reduction of fasting glucose to <70 mg/dL or an unintended reduction of weight >5%
- Pre-post change in safety measures (fasting glucose and weight)
- Number of AEs and SAEs

4.2 Secondary Endpoints

- Pre-post change in cognitive function
- Pre-post change in motor function

- Pre-post change in mood and apathy

4.3 Safety

- Incidence and severity of serious adverse events (SAEs) and adverse events (AEs)
- Frequency of change in clinically-significant vital signs, physical exam or neurological exam
- Plasma glucose level <70mg/dl
- Change in weight

5 Study Design

This study is a single center trial to determine dose finding, safety and tolerability of 3 doses of intranasal (IN) regular insulin (Table #2) and placebo in patients with Parkinson's disease.

Table 2: Intranasal Drug Dosing

Group	Drug	Dose	Volume	N=
Dose group 1	Insulin	20 IU/IN (10 IU, one nostril, twice daily)	100µl	7
Dose Group 2	Insulin	40 IU/IN (10 IU, each nostril, twice daily)	100µl	7
Dose Group 3	Insulin	80 IU/IN (20 IU, each nostril, twice daily)	200µl	9
Dose Group 4	Placebo	0.9% Saline (each nostril, twice daily)	200µl	7

After written informed consent has been obtained from the subject and family member/caregiver, subjects will be screened to assess study eligibility based on study inclusion/exclusion criteria. Subjects who are eligible at the end of the screening visit (Visit 1) will be scheduled for a baseline and randomization visit (Visit 2). During the baseline visit, subjects will be administered a cognitive battery. Subjects will also undergo a neurological examination, including the UPDRS (United Parkinson's Disease Rating Scale- MDS) to be performed in the "ON-STATE" (after taking Anti-Parkinson's medications according to the subject's regular medication schedule). A final safety/assessment visit will take place 3 weeks after visit 2 at which time the tests will be re-administered.

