7.1.2 Visit 2: Baseline/Initial Treatment Visit (Week 0)-fasting

The following procedures will be performed at this visit:

- Review Inclusion/Exclusion Criteria.
- Collect vital signs, orthostatic vital signs and weight.
- Collect concomitant medication information and record AEs/SAEs.
- Neuropsychological testing, including scales for mood, apathy and suicidality assessment (7.5)
- Perform UPDRS III
- Obtain laboratory studies, blood draw and glucose finger sticks
- Study Drug administration training (following cognitive testing).
- Hypoglycemia rescue training.
- Randomization of subject
- Administer first intranasal dose in clinic and provide study kit
- Visit 3 will be scheduled in 21 days (\pm 5 days).

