7.1.5 Visit 3: Final Treatment and Safety Visit (week 3)-fasting

The following procedures will be performed at this visit:

- Collect vital signs, orthostatic vital signs and weight.
- Collect concomitant medication information and record AEs/SAEs.
- Collect administration supplies, study diary, and remaining study drug
- Physical and neurological examination
- Neuropsychological testing, including scales for mood, apathy and suicidality assessment (7.5)
- Administer MoCA
- Perform UPDRS III

- Obtain laboratory studies

See **Table 3** for specific list of laboratory assessments

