13.6 Provision of Study Results and Information to Investigators

Study results will be made available by the study statistician once analysis (interim analysis) is complete. Study staff will not be unblinded in regards to individual subject's randomization status until after database lock.

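### Unless a redacted section provides a sham dose, one-nostril dosing lets staff who see it identify the 20 IU arm, so the stated double blind is not supported for that arm

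*Combined protocol and SAP*

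**What the plan says.** The Protocol Summary describes the design as "randomized, parallel-group, double blind, placebo-controlled". Section 13.6 adds "Study staff will not be unblinded in regards to individual" allocation before the database is locked.

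Table 2 in Section 5 gives the lowest dose group as "20 IU/IN (10 IU, one nostril, twice daily" and the placebo group as "0.9% Saline (each nostril, twice daily". The 40 IU and 80 IU groups also dose each nostril. The Protocol Summary repeats the same split, so it is not a slip in one table. There is one placebo group, and no placebo participant doses a single nostril.

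Staff meet the regimen, or may meet it, at these points:

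- Visit 2 (Section 7.1.2): "Administer first intranasal dose in clinic and provide study kit".
- Weeks 1 and 2 (Section 5.1): "Phone calls to assess compliance from study coordinator at weeks 1 and 2". Table 3 marks compliance and adverse events at the same two phone visits, and Section 7.1.3 has "Study staff phone call to address AEs/SAEs 1 week" after Visit 2.
- Visit 3 (Section 7.1.5): "Collect administration supplies, study diary, and remaining study drug", at the visit where AEs are recorded, UPDRS III is rated and the mood and apathy scales are completed.

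The readable text gives unblinded staff three roles: the product indicator (8.3), emergency blind breaks (8.2) and a seat on the DSMB (13.2). It does not say who supervises dosing. Sections 5.2 (administration with the device) and 5.3 (dose loading) are redacted.

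**The concern.** A double blind requires that nothing visible in the regimen separates the arms. Here the number of nostrils does. Anyone who knows the protocol and learns that a participant uses one nostril knows that the participant is on 20 IU of insulin and not on placebo.

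The count of AEs and SAEs is a primary endpoint (Section 4.1). It relies on what participants report, and Sections 11.1 and 11.2.1 leave the clinical significance of abnormal findings to the investigator. Section 12.2 compares AEs by group descriptively and tests a group only where a spike is noticed. UPDRS III is scored by a clinician (Section 7.4), the Apathy Scale is asked by an examiner (7.5.9) and the BDI-II is self-reported (7.5.8). Section 7.1.2 lists the baseline tests ahead of the first dose. If that order is followed, knowledge of the arm can enter only the follow-up side of a pre-post change.

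The trial aims to choose among three doses on safety and tolerability. Results for one of the three could be presented as double blind without that property.

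**Working it through.** **Inputs** (Table 2 and Protocol Summary):

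| Arm | n | IU per nostril | Nostrils | Daily dose = IU × nostrils × 2 | Listed volume |
|---|---|---|---|---|---|
| 20 IU | 7 | 10 | 1 | 10 × 1 × 2 = 20 | 100 µl |
| 40 IU | 7 | 10 | 2 | 10 × 2 × 2 = 40 | 100 µl |
| 80 IU | 9 | 20 | 2 | 20 × 2 × 2 = 80 | 200 µl |
| Placebo | 7 | saline | 2 | none | 200 µl |

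**1. The plan's own figures.** The arms sum to 7 + 7 + 9 + 7 = 30, the target accrual. All three dose labels reproduce. The 20 IU label works only with one active nostril: 10 IU in both would be 10 × 2 × 2 = 40 IU. The one-nostril entry is therefore meant as written.

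**2. What nostril count reveals to someone who knows the regimens.**

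- Before seeing any dosing: P(20 IU) = 7/30 = 23.3%.
- After seeing one-nostril dosing: P(20 IU) = 7/7 = 100%, and P(placebo) = 0.
- After seeing two-nostril dosing: P(20 IU) = 0, and P(placebo) moves from 7/30 = 23.3% to 7/23 = 30.4%. The other 16 of the 23 are 40 IU (7) and 80 IU (9). No individual two-nostril participant is identified by nostril count.

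**3. When it is revealed.** The first dose is taken in clinic at Visit 2. The week 1, 2 and 4 calls and Visit 3 all follow. A staff member who watched that dose would know the arm before any later AE contact and before the Visit 3 ratings.

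**4. With two-nostril dosing in every arm.** Nostril count carries no information, and P(20 IU) stays at 7/30 = 23.3%.

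**5. Size of a saline dummy.** One nostril, twice daily, for 21 days is 1 × 2 × 21 = 42 doses. At 0.1 ml each that is 4.2 ml per participant, and 7 × 4.2 = 29.4 ml for the arm.

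**The case against.** The strongest objection is the redaction. A sham actuation in the second nostril would naturally be described in Section 5.2 or 5.3, and neither can be read. Table 2 is a drug dosing table and need not list a sham. This stands as a condition on the whole point. It is not a full answer: Table 2 does list saline where saline is given as placebo, it shows insulin alone for the 20 IU group, and both places say one nostril without qualification. An unlisted saline sham looks unlikely but cannot be excluded.

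A reader might infer that participants are unblinded as well. The documents do not show this. A participant who doses one nostril learns the arm only if told that the other arms use two, and the consent form is not available.

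A reader might also infer that the listed 100 µl and 200 µl volumes expose the 40 IU or 80 IU arm. Whether a user or observer could see that difference depends on the redacted device loading, so masking between 40 and 80 IU cannot be judged from the visible text.

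The later contacts are weaker evidence than the first dose. The diary fields named in Section 5.1 are time, date, vial number and comments, not nostril. Nothing says that nostrils come up on the calls, and what returned supplies would show is unknown. At Visits 2 and 3 the AE item is listed before the first dose and before supply return, respectively. The plan also does not say that the person supervising the first dose later collects AEs or rates UPDRS III. These points narrow the exposure. They leave the first dose standing, with no readable text keeping it from staff who assess outcomes.

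Finally, the trial is small and descriptive (Sections 12.1 and 12.4). That limits what any comparison can show, but it does not make the blinding label accurate.

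**Conclusion.** The point holds, conditional on Sections 5.2 and 5.3 not already providing a sham dose. The visible regimen does not support the stated double blind for the 20 IU arm. That arm is 7 of 30 participants (23%), and each can be identified with certainty by staff who know the protocol and see or hear how the dose is taken, most clearly at the first dose in clinic.

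The outcomes open to influence are AE reporting and judgement and UPDRS III. The self-report scales are open chiefly if participants also know how the arms differ. Laboratory glucose and measured weight are not affected, nor is the randomisation.

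The percentages above measure how identifiable the arm is, not how far any result is biased. A reader might infer that 20 IU AE counts will be pushed up or down; the documents give no basis for a size or a sign, and none is claimed. Nor does the point show that the blind fails across the whole trial.

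**What to change.** Before first dosing, have every arm dose both nostrils from an identical kit with one labelled container per nostril. In the 20 IU arm the second container holds saline, 100 µl per dose. In the 40 and 80 IU arms both hold insulin, and in the placebo arm both hold saline. State this in Table 2 and the Protocol Summary. The two-container kit must go to all arms, because a second container in one arm alone would itself identify that arm. If Sections 5.2 and 5.3 already provide a sham, only the statement is needed.

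Cost: 4.2 ml of saline per 20 IU participant, 29.4 ml for the arm. Insulin doses, visits and n = 30 do not change. Downsides:

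- Each 20 IU participant takes 42 extra nostril doses (84 instead of 42 over 21 days).
- All arms need two containers.
- Containers could be mixed up. In the 20 IU arm, using one container for both nostrils would give a session dose of 0 or 2 × 10 = 20 IU instead of 10 IU. The upper figure is what the 40 IU arm receives at every session.

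If supply cannot change, describe the 20 IU arm as not masked to staff who see dosing, and do not report its AE and rated outcomes as double blind. In either case keep all by-group comparisons in Section 12.2.
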